9.3 Baseline

Obtain written informed consent from the subject's legally authorized representative prior to conducting any study-related testing that is not considered standard of care for valve procedures. All baseline tests must occur prior to the procedure. It is preferable if the testing is completed no more than one month prior to the procedure date.

The following baseline assessments are required:

- Medical history
- Physical exam
- Transthoracic echocardiogram
- Blood collection (Plasma free hemoglobin for Hemolysis evaluation). Spot urine urobilinogen is an acceptable alternative if a non-hemolyzed blood sample cannot be obtained.
- Anticoagulant/antiplatelet medication collection

For Adjunctive EU/CU Subjects, baseline assessments should be collected from subject's medical records, when available, for visits conducted prior to enrollment.

9.4 Procedure

The 15mm MHV is implanted surgically pursuant to the Instructions for Use.

The following assessments are required at the time of the procedure:

- Anticoagulant/antiplatelet medication collection
- Adverse event collection

For Adjunctive EU/CU Subjects, procedure assessments should be collected from subject's medical records, when available, for procedures conducted prior to enrollment.

9.5 Post-Procedure

If the subject does not have the 15mm MHV implanted the subject should be discontinued from the study and followed per the physician's standard of care.

As there are insufficient data to indicate otherwise, the sponsor recommends that subjects implanted with the 15mm MHV be routinely maintained on anticoagulants unless, for other reasons, it is not medically indicated.

The following assessments are required after the enrolled subject leaves the surgical suite with the valve implanted. These assessments must be completed at least 24 hours after the procedure:

- Physical exam

- Transthoracic echocardiogram
- Blood collection (Plasma free hemoglobin for Hemolysis evaluation). Spot urine urobilinogen is an acceptable alternative if a non-hemolyzed blood sample cannot be obtained.
- Anticoagulant/antiplatelet medication collection
- Adverse event collection
- Adverse event follow up

For Adjunctive EU/CU Subjects, post-procedure assessments should be collected from subject's medical records, when available, for visits conducted prior to enrollment.

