3.1 Study Duration

Each enrolled subject will be assessed at baseline, procedure, post-procedure, 30 days, six months, 12 months, and annually thereafter for as long as the valve remains implanted. Each enrolled subject will be followed for five years from the date of implant, until subject withdrawal, or until study closure, whichever occurs earliest.

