5 ENDPOINTS

5.1 Primary Safety Endpoint

The primary safety endpoint for this study is the actuarial (Kaplan-Meier) rate of total valve-related adverse events experienced through 365 days post implant or until the valve is removed/replaced due to anatomical growth of the subject, whichever occurs first. Valve-related adverse events to be evaluated are:

- Death
- Endocarditis
- Hemorrhage (whether or not due to anticoagulant/antiplatelet medication) [all and serious]
- Nonstructural dysfunction (including perivalvular leak [all and serious], hemolysis, and hemolytic anemia)
- Reoperation (including valve explant, not due to anatomical growth of the subject) [all and valve-related]
- Structural valve deterioration
- Thromboembolism
- Valvular thrombosis

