5.2 Primary Effectiveness Endpoints

The primary effectiveness endpoints in this study include the following:

1. Survival at 12 months post implant or survival until the valve is removed/replaced due to anatomical growth of the subject, whichever occurs first.
2. Peak gradient as assessed by echocardiography at 12 months post implant or when the valve is removed/replaced due to anatomical growth of the subject, whichever occurs first.
3. Mean gradient as assessed by echocardiography at 12 months post implant or when the valve is removed/replaced due to anatomical growth of the subject, whichever occurs first.

4. Valvular regurgitation as assessed by echocardiography at 12 months post implant or when the valve is removed/replaced due to anatomical growth of the subject, whichever occurs first.

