6 STATISTICAL ANALYSIS

6.1 Statistical Analysis and Reporting

Kaplan-Meier adverse event rates with 95% confidence intervals and early rates will be calculated for all safety and survival endpoints.

Hemodynamic function will also be evaluated at each visit for each of the following variables:

- Mean pressure gradients across the mitral valve
- Peak pressure gradients across the mitral valve
- Cardiac output
- Cardiac index
- Valvular regurgitation (and the site, as appropriate)

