9.2 Assessment Schedule

All enrolled subjects will be assessed according to the following schedule for as long as the valve is implanted.

Table 1: Assessment Schedule

ASSESSMENTS	Baseline	Procedure	Post-Procedure ¹ (+ 24 hours)	30 Days ¹ (± 14 days)	6 Months ¹ (± 30 days)	12 Months ¹ (± 60 days)	Annual Visits through 60 Months ¹ (± 60 days)	Explant (Prior to procedure)
Medical History	X							
Physical Exam (PE)	X		X	X	X	X	X	X
Transthoracic Echocardiogram (TTE) ²	X		X	X	X	X	X	X
Blood Collection ³	X		X	X	X	X	X	X
Anticoagulant/Antiplatelet Medication Collection	X	X	X	X	X	X	X	X
Adverse Event Collection ⁴		X	X	X	X	X	X	X
Adverse Event Follow-up ⁵			X	X	X	X	X	X

1. Visits are to occur as long as the valve remains implanted.
2. The study specifies TTE rather than transesophageal echocardiography (TEE) to minimize subject risk. Echocardiographic data collected from TEE warranted for any other medical purpose is allowed.
3. Plasma free hemoglobin for hemolysis evaluation. Spot urine urobilinogen is an acceptable alternative if a non-hemolyzed blood sample cannot be obtained.
4. Refer to section 15.2 for a list of adverse events that are required to be collected and reported.
5. Required only for subjects who have an unresolved adverse event.

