9.7 Additional Follow-up

Protocol required follow-up visits should be completed by the Investigator. To aid in subject follow-up compliance, subjects can return to their primary cardiologist for follow up visits but data must be obtained by the Investigator for review and submission to the Sponsor.

Investigators should inform cardiologists of all required follow-up tests prior to the visit and every effort should be made to obtain complete tests results with all required data points after the visit occurs. Protocol deviations will be required for all missed testing (refer to section 17.2.5 Protocol Compliance).

The following assessments are required at follow-up visits at the intervals noted on the assessment schedule in section 9.3 for all enrolled subjects that have the valve implanted:

- Physical exam
- Transthoracic echocardiogram
- Blood collection (Plasma free hemoglobin for Hemolysis evaluation). Spot urine urobilinogen is an acceptable alternative if a non-hemolyzed blood sample cannot be obtained.
- Anticoagulant/antiplatelet medication collection
- Adverse event collection
- Adverse event follow-up

For Adjunctive EU/CU Subjects, additional assessments should be collected from subject's medical records, when available, for visits conducted prior to enrollment.

10 Discontinuation

Subjects must be informed about their right to withdraw from the study at any time and for any reason without sanction, penalty, or loss of benefits to which the subject is otherwise entitled. Withdrawal from the study will not jeopardize the subject's future medical care or relationship with an Investigator. All reasonable efforts should be made to retain the subject in the clinical study until study completion. Subjects will be asked what the reason for termination/withdrawal is but have the right not to answer.

The Principal Investigator may also withdraw a subject from the study at any time if he/she believes it is in the subject's best interest.

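### After a failed implant attempt, section 9.5 discontinues the subject with no active search for later events or deaths, and the endpoints give such a subject no time zero or denominator

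*Combined protocol and SAP*

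**What the plan says.** **Who leaves the study.** Section 9.5: "If the subject does not have the 15mm MHV implanted the subject should be discontinued from the study". Care then follows the physician's usual practice. The rule applies to all arms and gives no time at which discontinuation takes effect.

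**What is collected afterwards.** The post-procedure assessments in 9.5 apply "after the enrolled subject leaves the surgical suite with the valve implanted". Section 9.2 sets the schedule on the same condition: "All enrolled subjects will be assessed according to the following schedule for as long as the valve is implanted". Section 9.7 requires later visits "for all enrolled subjects that have the valve implanted".

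**What is captured regardless.** Adverse events are collected at the procedure (9.4). Surveillance starts at enrollment, or at the attempted implant for EU/CU subjects, and unresolved events are followed until they resolve (15.2.2). SAEs are reported within 3 calendar days of site awareness (15.2.1), and deaths during the study are reported (15.2.4). Surveillance stops when the subject's participation concludes (15.2.2).

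**How it is analysed.** Section 3.1: "Each enrolled subject will be followed for five years from the date of implant". Section 5.1 counts "total valve-related adverse events experienced through 365 days post implant", or until removal for growth. The first item of 5.2 is "Survival at 12 months post implant or survival until the valve is removed/replaced due to anatomical growth of the subject". Section 6.1 promises Kaplan-Meier rates, and "early rates will be calculated for all safety and survival endpoints". It names no analysis set.

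**Attempts.** Section 8.2.3 defines an attempt as contact between the device and the child's heart, and admits EU/CU subjects on that basis.

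**The concern.** This is a single-arm study meant to support a PMA supplement (3, 4.1). Whether the valve ends up in place is known only after treatment has begun, so removing children in whom it does not selects on a post-treatment outcome. No control arm would reveal the effect. A bleed, embolus or death in the days after a failed attempt, possibly while the child is still in hospital, could be missed. It could also be known to the site but have no defined place in the early rates and survival estimates.

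The concern is limited to attempted implants. Section 9.5 also covers enrolled children whom the device never touched, and nothing is lost for the device's safety record by discontinuing them. Gradients and regurgitation need the valve in place and are unaffected.

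**Working it through.** The documents state no sample size, number of failed attempts or performance goal, so there is no figure to reproduce. The check is a reading of the sections together, followed by an illustration on assumed counts.

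**1. Capture.** Take a child with a failed attempt who is discontinued and has a new event some days later.
- 9.4 covers the procedure itself, so it does not reach the event.
- 9.2, 9.5 and 9.7 require an implanted valve, so no visit is due.
- Follow-up to resolution (15.2.2) applies to events already open, so it does not reach a new one.
- 15.2.1 and 15.2.4 may reach it if the site learns of it, and 15.2.4 also depends on whether a death after discontinuation counts as during the study. Neither makes anyone look.

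What is missing is therefore active ascertainment after discontinuation.

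**2. Analysis.** Sections 3.1, 5.1 and 5.2 all count from implant. A child with an attempt but no implant has no such date, and 6.1 does not say whether that child is in the denominator. The EU/CU start at attempted implant in 15.2.2 is a reporting start, not an analysis origin. Even a death during the procedure, which is captured, has no stated place in the estimates.

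**3. Which endpoints.** Survival in 5.2 is all-cause, so any death matters. Section 5.1 counts valve-related events. Hemorrhage, thromboembolism and death can occur without the valve in place, but they count there only if adjudicated valve-related. The definitions of the other five event types in Appendix 11 depend on the study valve.

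**4. Illustration.** Assume n attempts, one failed, and d = 1 early death among the n − 1 implanted. Let x = 1 if the failed-attempt child dies early and 0 otherwise. Section 6.1 does not define early; 30 days is assumed.

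Implanted-only rate = d/(n − 1). By-attempt rate = (d + x)/n. If the failed-attempt child dies with probability p, the expected by-attempt rate is (d + p)/n. For p, section 7.2 gives about 5% to 30% for pediatric mitral replacement; that range is not specific to 30 days or to failed attempts.

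| n | Implanted-only | By attempt, x = 0 | By attempt, x = 1 | Expected, p = 5% to 30% |
|---|---|---|---|---|
| 10 | 1/9 = 11.1% | 1/10 = 10.0% | 2/10 = 20.0% | 10.5% to 13.0% |
| 20 | 1/19 = 5.3% | 1/20 = 5.0% | 2/20 = 10.0% | 5.25% to 6.5% |
| 30 | 1/29 = 3.4% | 1/30 = 3.3% | 2/30 = 6.7% | 3.5% to 4.3% |

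The expected by-attempt rate exceeds the implanted-only rate only if p > d/(n − 1), which is 5.3% at n = 20. The direction therefore depends on an unknown. Exact 95% intervals are wide and overlap: 0.1% to 26.0% for 1/19 and 1.2% to 31.7% for 2/20.

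**5. Why a new analysis set alone is not enough.** Suppose discontinuation took effect on the procedure day, which 9.5 does not state. In a Kaplan-Meier analysis of all 20 attempts, the failed-attempt child would be censored at time zero. The day-30 estimate would be 1/19 = 5.3% whether that child later lived or died. The attempted set is informative only if follow-up extends past discontinuation.

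**The case against.** The strongest reply is that little is lost. Surveillance begins at enrollment or attempt, procedural events are collected, open events are followed, and the site must report SAEs it knows of and deaths during the study. The investigators are experienced implanting surgeons (7.3), who would usually know of an early in-hospital death or bleed. This stands in part. It narrows the gap to events that nobody is asked to look for, but does not close it.

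A second reply is that the plan implies an implanted population: every clock starts at implant, and 4.2 evaluates the objective while the valve remains in place. That is a fair guess, and the fix keeps that set primary. But 6.1 does not say so, and EU/CU entry and surveillance are based on the attempt.

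Third, the illustration depends on what happens to one child. At the protocol's own mortality range the expected shift at n = 20 runs from about zero to +1.2 percentage points. This stands. Failed attempts could carry higher mortality, but no document says so.

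A reader might also infer that 8.2.3 contradicts 9.5, because item 4(a) asks for follow-up per the schedule while 9.2 and 9.5 provide none without a valve. The text does not go that far. Item 3 makes prospective follow-up conditional on its being applicable, item 4(a) may ask only for what the protocol otherwise requires, and the explanted status in item 4(b) can be read to include removal at the same operation. It is an ambiguity that needs resolving.

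**Conclusion.** The concern holds in limited form. Under 9.5 as written, new events and deaths after a failed attempt have no active ascertainment, and an attempt without an implant has no stated time zero or denominator. The main exposure is all-cause survival and the early rates. On the assumed counts at n = 20, by-attempt early mortality is 5.0% to 10.0% against 5.3% in the implanted, with an expected value of 5.25% to 6.5% at the protocol's mortality range. If there were no failed attempts, the effect is zero.

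Three stronger readings are not supported. The plan does not lose all events in these children, because 9.4 and 15.2 capture some. It does not leave three of the eight event types in 5.1 wholly exposed, because those count only when adjudicated valve-related. Nor can one say that the results are biased in the device's favour: the direction is unknown, and 9.5 does not say when discontinuation takes effect. The point is complete reporting, not a changed decision, and it is worth correcting because the correction is cheap.

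**What to change.** 1. **Section 9.5.** For subjects with an attempt (8.2.3 definition) but no implant, defer discontinuation until adverse events and vital status have been collected through discharge or 30 days, and state which. Apply this prospectively and as data collection only, with clinical care unchanged.
2. **Section 6.1.** Name the implanted set as primary. Beside it, report a supportive attempted-implant set, with time zero at the first attempt, for procedural and early adverse events and survival. Give attempt success as n/N.
3. **Section 8.2.3.** Clarify how items 4(a) and 4(b) apply to a living EU/CU child not left with the valve, and reconcile them with 9.2 and 9.5.

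The cost is wording changes that may need FDA and IRB review under 17.1.2, possibly consent wording, and a short record check for each failed attempt. Attempts should be identified from procedure records. Valve returns under 14.3 are not enough, because they also include valves that never touched the anatomy. Early rates may come out slightly less favourable, and outcomes after a failed attempt partly reflect another prosthesis, which is why the attempted set is supportive only.

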9.6 Post-Procedure Anticoagulation Recommendation

As there are insufficient data to indicate otherwise, the sponsor recommends that patients implanted with the 15mm MHV be routinely maintained on anticoagulants to avoid the risk of thrombus formation and thromboembolic complications, unless it is not medically indicated.

The recommended anticoagulation therapy for patients implanted with the 15mm MHV are based on the 2013 AHA Guidelines for the Prevention and Treatment of Thrombosis in Pediatric Patients²⁴ in combination with experience from subjects previously enrolled in this study.

Acceptable forms of anticoagulants include intravenous unfractionated heparin or oral warfarin. When using warfarin the recommended target INR is 2.5 to 3.5 for valves implanted in the mitral position in the absence of risk factors for thrombus formation. In the presence of risk factors consider using a higher target INR or adding aspirin to therapeutic warfarin. Risk factors include first 3 months post-implant, younger age (< 6 months), small size (<6 kg), low flow state, unreliable oral intake, previous thromboembolism, and hypercoagulable condition. Home INR monitoring may be associated with a reduced rate of complications. Use of low molecular weight heparin may be associated with an increased rate of complications based on input from HALO IDE investigators.

In patients receiving warfarin, the INR should be monitored daily until therapeutic levels are achieved, and then may be decreased in frequency when stable with a minimum of monthly testing. The INR should be tested whenever there is illness or with any changes in medication or diet.

The final choice for anticoagulation therapy is left to the clinical judgement of the investigator.

9.7 Additional Follow-up

Protocol required follow-up visits should be completed by the Investigator. To aid in subject follow-up compliance, subjects can return to their primary cardiologist for follow up visits but data must be obtained by the Investigator for review and submission to the Sponsor.

Investigators should inform cardiologists of all required follow-up tests prior to the visit and every effort should be made to obtain complete tests results with all required data points after the visit occurs. Protocol deviations will be required for all missed testing (refer to section 17.2.5 Protocol Compliance).

The following assessments are required at follow-up visits at the intervals noted on the assessment schedule in section 9.3 for all enrolled subjects that have the valve implanted:

- Physical exam
- Transthoracic echocardiogram
- Blood collection (Plasma free hemoglobin for Hemolysis evaluation). Spot urine urobilinogen is an acceptable alternative if a non-hemolyzed blood sample cannot be obtained.
- Anticoagulant/antiplatelet medication collection
- Adverse event collection
- Adverse event follow-up

For Adjunctive EU/CU Subjects, additional assessments should be collected from subject's medical records, when available, for visits conducted prior to enrollment.

10 Discontinuation

Subjects must be informed about their right to withdraw from the study at any time and for any reason without sanction, penalty, or loss of benefits to which the subject is otherwise entitled. Withdrawal from the study will not jeopardize the subject's future medical care or relationship with an Investigator. All reasonable efforts should be made to retain the subject in the clinical study until study completion. Subjects will be asked what the reason for termination/withdrawal is but have the right not to answer.

The Principal Investigator may also withdraw a subject from the study at any time if he/she believes it is in the subject's best interest.

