15.2.2 Reporting Valve-Related Adverse Events

Safety surveillance within this trial (and the safety reporting performed by the investigator) starts:

- as soon as the subject is enrolled for Pivotal IDE subjects enrolled under protocol revision A or B.
- as soon as the subject is enrolled for Adjunctive Prospective Subjects.
- from the time of attempted initial implant (defined as the device physically contacting the subject's cardiac anatomy) for enrolled Adjunctive EU/CU Subjects.

Safety surveillance and safety reporting will continue until the last study visit has been performed, or the subject is deceased, or the subject concludes participation in the trial.

Investigators are responsible for promptly reporting, as soon as they become aware, all serious and non-serious valve-related adverse events as specified in Akins et al.²⁵ to the sponsor by

completing the Adverse Event CRF. Serious adverse events should be reported as specified in Section 15.2.1. Reportable events include:

- Death
- Endocarditis
- Hemorrhage (whether or not due to anticoagulant/antiplatelet medication)
- Nonstructural dysfunction (including perivalvular leak, hemolysis, and hemolytic anemia)
- Reoperation (including valve explant, not due to anatomical growth of the subject)
- Structural valve deterioration
- Thromboembolism (valve-related)
- Valvular thrombosis
- Unanticipated Adverse Device Effects (UADEs)

Refer to Appendix 11 for definitions of all reportable valve-related adverse events. All unresolved adverse events should be followed by the Investigator until resolution. Updates to adverse events should be provided to the sponsor by completing the AE Follow-Up CRF.

The sponsor may request that additional information such as operative notes, clinic notes, discharge summaries, histopathology reports, or a physician's summary of the event be provided to the sponsor as supporting documentation for all reported events.

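### Events after an investigator-initiated withdrawal with the valve in place are not collected, so 12-month survival and the 365-day event rate can be informatively censored

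*Combined protocol and SAP*

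**What the plan says.** Section 10 (Discontinuation) of the combined protocol and SAP gives the investigator an open discretion: "The Principal Investigator may also withdraw a subject from the study at any time if he/she believes it is in the subject's best interest". It does not ask whether the study valve is still implanted.

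Three other sections decide what happens next.

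- Section 3.1: "Each enrolled subject will be followed for five years from the date of implant, until subject withdrawal, or until study closure, whichever occurs earliest".
- Section 15.2.2: "Safety surveillance and safety reporting will continue until the last study visit has been performed, or the subject is deceased, or the subject concludes participation". A later paragraph of the same section adds: "All unresolved adverse events should be followed by the Investigator until resolution".
- Section 15.2.4 asks for reports of deaths that occur during the study.

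Table 1 in section 9.2 has an explant column but none for withdrawal or for any contact after it.

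Two primary results depend on complete ascertainment over the first year. The safety endpoint in 5.1 is "the actuarial (Kaplan-Meier) rate of total valve-related adverse events experienced through 365 days post implant", and its components include death and reoperation. The first effectiveness endpoint in 5.2 is "Survival at 12 months post implant or survival until the valve is removed/replaced due to anatomical growth of the subject, whichever occurs first". Section 6.1 says how they are analysed: "Kaplan-Meier adverse event rates with 95% confidence intervals and early rates will be calculated for all safety and survival endpoints". No censoring rule for withdrawal and no sensitivity analysis are stated.

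**The concern.** The device is an implant, so withdrawing a child from the study does not end exposure to it. It ends data collection only. With follow-up closed at withdrawal, the natural Kaplan-Meier handling is to censor the child there. That is unbiased only if withdrawn children have the same later risk as those who stay.

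A best-interest judgement refers to the child's own situation, so equal risk cannot be taken for granted. If withdrawn children are at higher risk, survival is overstated and the event rate understated. Unlike a family's refusal of further data use, an investigator's decision to stop study visits does not in itself mean that consent to use records has been revoked. Some of the loss may therefore be avoidable.

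**Working it through.** **1. Can a new event after withdrawal reach the analysis?**

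| Step | Section | Result |
|---|---|---|
| Withdrawal with valve in place | 10 | Allowed at any time |
| Follow-up after withdrawal | 3.1 | Ends |
| Surveillance for new events | 15.2.2 | Ends when participation concludes |
| Events already open | 15.2.2 | To be followed to resolution; no exception for withdrawal stated |
| Deaths | 15.2.4 | Reportable if during the study |
| Visit or status check at or after withdrawal | 9.2, Table 1 | None |

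Under the stated rules, a new event after withdrawal has no route into the 5.1 or 5.2(1) rates. An event already open may still have one.

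**2. How far could this move a 12-month rate?**

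The visible text gives no sample size, withdrawal rate or performance goal, so there is no figure in the plan to reproduce. All inputs below are assumptions.

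Assume N = 20, first events on days 30, 100 and 200, and two children withdrawn on day 90.

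- Day 30: 20 at risk, factor 19/20. Then 19 remain, and 17 after the withdrawals.
- Day 100: factor 16/17. Day 200: factor 15/16.
- Kaplan-Meier event rate = 1 − (19/20)(16/17)(15/16) = 1 − 0.838 = 16.2%.
- Neither withdrawn child has an event by day 365: 3/20 = 15.0%.
- Both do: 5/20 = 25.0%.

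The Kaplan-Meier rate can thus be up to 25.0 − 16.2 = 8.8 points too low, or 16.2 − 15.0 = 1.2 points too high.

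Other assumed cases, with two withdrawals before day 365 and observed events split evenly around them (a single event falls after):

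| N | Observed events | Kaplan-Meier | Neither / both withdrawn children have an event |
|---|---|---|---|
| 20 | 1 | 5.6% | 5.0% / 15.0% |
| 20 | 6 | 32.0% | 30.0% / 40.0% |
| 50 | 2 | 4.1% | 4.0% / 8.0% |

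**3. What if later risk differs by a given factor?**

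This is an exponential model. A share of children is withdrawn at a uniform time in year one, and their hazard afterwards is HR times the hazard before. True rates were chosen within the 5 to 30% mortality range cited in section 7.2.

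| True 12-month rate | Withdrawn | HR | Kaplan-Meier limit |
|---|---|---|---|
| 15% | 10% | 1 | 15.0% |
| 15% | 10% | 3 | 13.8% |
| 15% | 10% | 5 | 13.0% |
| 15% | 10% | 10 | 11.5% |
| 30% | 20% | 5 | 24.0% |

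With HR = 1 the expected bias is nil. It grows with the share withdrawn and with the excess risk.

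**The case against.** A reader might infer that deaths and reoperations are in fact being lost and that the primary rates are biased downward. The documents do not support that. They give no withdrawal counts. Bias needs a child withdrawn before day 365 whose later risk differs from that of the children who remain. That the sickest child is the one most likely to be withdrawn is plausible, but nothing in the text shows it.

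Four further points narrow the concern.

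- **First events.** On a first-event reading of 5.1, a child withdrawn after a qualifying event is already counted, and later censoring cannot lower that rate. This stands for 5.1. It does not protect 5.2(1), where the same child is still at risk of death.
- **Open events.** Because 15.2.2 has unresolved events followed to resolution, it is too strong to say that all surveillance ends. A death or reoperation arising from an open event could be captured. The section does not say which of its two sentences governs after withdrawal.
- **Less need to withdraw.** Section 10 asks for reasonable retention efforts, and 9.7 lets the child be seen by the primary cardiologist, so burdensome visits need not lead to withdrawal. This may make withdrawals fewer, but it collects nothing once one has happened. Section 14.3 asks for explanted valves to be returned, which might reveal some explants, but that is device handling and not endpoint collection.
- **Consent.** The consent form is not among the pages available. It may already allow, or restrict, access to records after withdrawal. Any fix has to be conditional on it.

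Withdrawal by the family opens the same gap, so the investigator's discretion is not its only source.

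**Conclusion.** The concern holds as a gap in the collection rules that can bias two primary results. It does not hold as a demonstrated bias. Under the stated rules, new events after withdrawal and before day 365 are not recorded. The exposed results are 12-month survival and, for children with no earlier qualifying event, the 365-day event rate. If withdrawn children are at higher risk, both look too favourable. If risk is unrelated to withdrawal, the expected bias is nil.

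The size cannot be established from the documents. In the assumed cases with 20 children and two withdrawals, the most Kaplan-Meier could understate the rate is about 8 to 9 points (8.0, 8.8 and 9.4). The modelled 10%-withdrawn cases give 1.2 to 3.5 points for HR 3 to 10. This reasoning assumes censoring at withdrawal, which 3.1 and 6.1 imply but do not state, and a first-event reading of 5.1. The change is worth making because it is cheap and because status not collected at the time may not be recoverable later.

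**What to change.** 1. In section 10, separate ending study visits and tests from ending data collection. Unless the legally authorized representative withdraws consent for data use, and as far as the consent allows, the site continues to record vital status, valve status (in place, reoperated, explanted) and the 15.2.2 events. The source is medical records or the treating cardiologist, through 12 months and then annually.
2. Require the investigator's own reason for withdrawal to be recorded. At present only the subject is asked, and may decline to answer.
3. Align 3.1, 15.2.2 and 15.2.4 with this. In 15.2.2, reconcile the sentence on when surveillance ends with the sentence on following unresolved events.
4. In section 6.1, state that children of unknown status are censored at last contact. Report the 5.1 and 5.2(1) rates also with all such children counted as events and with all counted as event-free. The worst case alone would give only one bound.

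The cost is small: a little site effort for what should be a few children, amendment review under 17.1.2, possibly a consent revision, and one extra sensitivity range. The data route already exists, since 9.7 has the investigator obtain data from the primary cardiologist, and medical-record data are already accepted for Adjunctive EU/CU Subjects.
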